## STUDY RATIONALE

### COMMUNICATION IN THE CRITICALLY ILL

Critically ill patients, who are mechanically ventilated, suffer not only from their acute, potentially devastating illness, but also from the lack of ability to communicate in an effective manner. This is the direct result of the orotracheal tube or tracheostomy required for the mechanical ventilation, which does not allow speech to be produced. On top of the mechanical change in air flow, communication challenges result from sedation, neurological injuries (primary brain injury or secondary encephalopathy), and delirium.

Lack of communication can lead to increased frustration (Guttermson et al., 2014), anxiety, and overall psychological stress (Carruthers et al., 2017) and could continue to the development of post-traumatic stress disorder (PTSD) (Wade et al., 2012). On top of the subjective discomfort, the inability to communicate in an effective manner may impair medical care—for example, by failure to assess symptoms such as pain (Chanques et al., 2014) or breathing discomfort (Binks et al., 2017) by behavioral cues only.

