We found that 27.8% of admissions to the ICU were intubated for at least 48 hours, while 18.9% were intubated for at least three days and 12.6% were intubated for at least five days. The mean number of ventilator days for patients ventilated for at least two days was 8.6, and 11.6 and 16.2 for patients ventilated for at least three and five days, respectively. Given the high mean number of ventilation days for the patients who are ventilated for at least two days, it seemed reasonable to further analyze this group as a the inclusion criterion. We further found that nearly 25% of the patients ventilated for at least two days had recorded RASS of -1 to 1 for at least two days, suggesting a window in which these patients could potentially communicate (see Figure 1A for breakdown by units). It was also found that 17.9% of patients ventilated for at least two days ended up being ventilated long- term, requiring a tracheostomy (see Figure 1B for breakdown by units). We hypothesize that this group, those who will need to be on the ventilator for a long period of time, will be the patient population that will mostly benefit from a wearable, eye-tracking-based communication device. At Emory, by this retrospective analysis of the past three years, we are estimated to screen about 130 patients per month who are ventilated for at least two days.

**Figure 1:** Breakdown of patients by units who are ventilated for at least two days and have RASS between -1 to 1 for at least two days (A) and patients who ended up requiring tracheostomy (B).

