### INCLUSION CRITERIA

- Intensive Care Unit (ICU) Admission
- Mechanically ventilated for at least 24 hours
- RASS between -1 to 1 at the time of screening (Note: minimal sedation is allowed including low-dose Fentanyl, Dexmedetomidine, Ketamine, Propofol, etc., as long as the RASS is in the predefined range).

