## SAMPLE SIZE

From our retrospective analysis (described in the introduction), we expect about 130 patients per month for the initial screening (ventilated for at least two days). The same patient could be ineligible on a certain day, but become eligible later in the admission (e.g., due to the severity of the illness, the patient is deeply sedated for the first few days, and later sedation is weaned). This will allow us to recruit more patients, at different time points of their admission. Even with this in mind, it would be reasonable to assume that about half of these initially screened patients will not be eligible at any point of their admission due to any one of the exclusion criteria. Of those who will be eligible, we expect a high rate of consent, due to the low risk and the potential benefit of using the device while in the ICU. We therefore expect a rate of about 30 patients a month to be enrolled.

For the first step, we will plan to enroll up to 60 patients, and at least a third of the sample will be from the neuroscience ICU, and specifically patients with an acute brain injury

Given that there are no prior data, there is no clear criteria that would justify a specific number. We believe that having 40 to 60 patients work with this new device would be sufficient to draw initial conclusions about its use and specific indications according to the study aims as stated above.

For the second part of the trial, power calculations are based on previously published BRAIN-ICU trial. In that observational trial patients had  $6.8 \pm 5.2$  delirium/coma-free days within the first 14 days of admission, with an overall rate of about 50% rate of delirium. For the present trial, we considered a 2 day reduction in the time spent delirious as clinically significant. Given these parameters, the present trial will require 248 patients ( $N = 124$  per arm) to achieve sufficient power (80%,  $\alpha = .05$ ) to detect a 2 day difference. In general, a sample size of 248 will provide sufficient power to detect a standardized mean difference of 0.38 (assuming minimal asymptotic relative efficiency of Mann-Whitney U test), an odds ratio of 2.14 for binary variables (assuming maximal variance for a binomial distribution), and a Cohen's  $f$  of 0.18.

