### Step 2:

Primary Outcome: The time spent alive and non-delirious in the ICU

Covariates/Confounders: age, gender, race, baseline education level, unit to which the patient was admitted to, need for tracheostomy, severity of illness by SOFA or APACHE score on admission and randomization day, categorical reason for admission (e.g. sepsis, ARDS, elective surgery, stroke etc), diagnosis of delirium prior to randomization and the presence of an acute central neurological injury.

Unadjusted Analyses: The time spent alive and non-delirious in the ICU will be evaluated using the stratified variant of the Mann-Whitney U test. In this analysis, patients will be stratified by ICU setting. For other variables, the unadjusted comparison will depend on the type of variable. In general, continuous variables will be compared using a Mann-Whitney U test and categorical variables will be compared using the  $\chi^2$  test.

Adjusted Analyses: The time spent alive and non-delirious in the ICU will be evaluated using a multi-level/mixed-effects quantile regression (median/50th percentile) while controlling for the previously listed covariates. The multi-level/mixed-effects model will be used to account for clustering within ICU setting. In the event that the regression fails to estimate properly, the covariates will be used to generate propensity scores and patients will be stratified into  $\geq 5$  propensity score strata. The time spent alive and non-delirious in the ICU will then be analyzed using the stratified variant of the Mann-Whitney U test. Analyses of the secondary outcomes will depend on the type of variable. Continuous variables will be analyzed using multi-level/mixed-effects quantile regressions (median/50th percentile), binary variable will be analyzed using multi-level/mixed-effects binary logistic regressions, ordinal scales will be analyzed using multi-level/mixed-effects ordinal (cumulative logit) logistic regressions.

Missing Data: In the event of substantial missing data, data will be imputed using a multiple imputation procedure. The type of procedure (e.g. fully conditional specification, hot decks etc.) and the number of imputed data sets will be determined by the amount of missing data and the pattern of missingness.

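### The adjusted primary analysis includes need for tracheostomy with no time point, so tracheostomies after randomization can enter the median regression and its propensity-score fallback

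*Combined protocol and SAP*

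**What the plan says.** The Statistical Analysis Plan, Step 2, gives one list of covariates for the adjusted analyses. It includes "need for tracheostomy, severity of illness by SOFA or APACHE score on admission and randomization day" and ends with "diagnosis of delirium prior to randomization and the presence of an acute central neurological injury". Three items carry a time: education is a baseline level, severity is scored on two named days, and delirium must precede randomization. Tracheostomy and acute central neurological injury carry none.

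The whole list enters a mixed-effects median regression of the primary outcome. If that model cannot be fitted, "the covariates will be used to generate propensity scores and patients will be stratified into" five or more strata for a stratified Mann-Whitney test. The unadjusted analysis is a Mann-Whitney test stratified by ICU only. The plan calls neither the unadjusted nor the adjusted analysis primary.

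Other sections bear on when a tracheostomy may happen:

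- Inclusion Criteria: "Mechanically ventilated for at least 24 hours".
- How Many Patients Would Benefit from a Communication Device?: in the site's 2016 to 2018 data, "17.9% of patients ventilated for at least two days ended up being ventilated long- term, requiring a tracheostomy".
- Communication in the Critically Ill: loss of speech is the "direct result of the orotracheal tube or tracheostomy required for the mechanical ventilation", so some patients may already have a tracheostomy when enrolled.
- Sample Size: late enrolment is expected, for example where "the patient is deeply sedated for the first few days, and later sedation is weaned".

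The documents give no distribution of tracheostomy times.

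**The concern.** A covariate measured before randomization cannot be affected by the arm, so adjusting for it leaves the effect of assignment intact and may add precision. A tracheostomy after randomization has no such protection. If the device changes who gets one, adjusting for it does harm in two ways. It removes any part of the device's effect that runs through tracheostomy. It also compares patients who differ in unmeasured severity, because those who needed a tracheostomy despite the device are not like those who needed one without it.

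The propensity fallback has the same fault in another form. With randomized arms, a propensity score on baseline variables reflects only chance imbalance. Once a variable affected by the arm is included, the strata are partly defined by a consequence of treatment.

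At stake is the adjusted result for the primary outcome. If it disagreed with the unadjusted test, the reader could not tell whether the cause was chance imbalance or adjustment for an event after randomization, and the plan does not say which result decides.

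**Working it through.** **1. Can the variable include events after randomization?** Yes. It has no date, three items in the same list do, and no other section supplies one. Entry is possible at 24 hours of ventilation, the outcome runs for up to 14 days from randomization, and the site's data describe tracheostomy as the end of a long course. At 17.9%, about 0.179 × 248 = 44 patients would have one at some time. The share after randomization is unknown.

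**2. The plan's own sample size.** Inputs from Sample Size: difference 2 days, SD 5.2, power 80%, α = 0.05 (taken as two-sided), minimal efficiency of the Mann-Whitney test (taken as the standard bound 0.864, which the plan does not print).

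- 2 × [5.2 × (1.960 + 0.842)/2]² = 106.1, so 107 per arm.
- 107/0.864 = 123.8, so 124 per arm and 248 in total.

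This matches the plan. The calculation is for an unadjusted two-group comparison, so changing the covariate list leaves it alone. For scale, the standard error of a mean difference is 5.2 × √(2/124) = 0.66 day.

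**3. Illustration of the bias.** From the documents: total effect 2.0 days, SD 5.2, control tracheostomy 17.9%. The rest is assumed:

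- Every tracheostomy falls after randomization.
- Severity U is standard normal and unmeasured.
- logit P(tracheostomy) = a + b·U + log(OR)·arm, with b = 0.5 or 1.0 and a set to give 17.9% in controls.
- The outcome is linear in arm, tracheostomy (0, 2 or 4 days lost) and U (correlation 0.2 or 0.5), normal and unbounded. The direct effect is set so that the total is 2.0.

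This makes 12 settings per odds ratio, with 600,000 patients each. The unadjusted difference was 1.97 to 2.02 throughout.

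| Tracheostomy OR, device vs control | Adjusted effect, least squares (days) | Five propensity strata (days) |
|---|---|---|
| 1.0 | 1.98–2.02 | 1.99–2.03 |
| 0.7 | 1.76–1.99 | 1.78–1.99 |
| 0.5 | 1.52–1.95 | 1.67–1.96 |
| 0.3 | 1.32–1.92 | 1.61–1.96 |
| 1.4 | 2.02–2.29 | not run |
| 2.0 | 2.07–2.67 | not run |

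Repeating the least-squares runs moved the limits by at most 0.03 day. Median regression on 60,000 patients, without an ICU random effect, gave 1.48 to 1.94 at an odds ratio of 0.5 (sampling noise about 0.1 day). The propensity column uses 5 settings per odds ratio, 300,000 patients each, and a score built on three noise covariates plus tracheostomy.

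At an odds ratio of 0.5 the least-squares shift from 2.0 is 0.05 to 0.48 day, or 0.05/0.66 = 0.1 to 0.48/0.66 = 0.7 standard errors.

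**4. A second model.** Median regression, 200,000 patients per scenario, with unmeasured severity costing 3 days per SD and b = 1.0:

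| OR | No effect on outcome: adjusted | Direct effect 2 days, tracheostomy harmless: unadjusted → adjusted | Direct effect 1.5 days, tracheostomy costs 4 days: unadjusted → adjusted |
|---|---|---|---|
| 1.0 | 0.01 | 1.95 → 1.96 | 1.52 → 1.50 |
| 0.75 | −0.06 | 1.97 → 1.87 | 1.68 → 1.47 |
| 0.5 | −0.20 | 1.98 → 1.81 | 1.78 → 1.36 |
| 0.33 | −0.27 | 2.04 → 1.76 | 1.90 → 1.27 |

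The last column shows both mechanisms. At 0.5 the tracheostomy rates were 17.8% and 10.6%, so the total effect should be about 1.5 + 4 × (0.178 − 0.106) = 1.79; the simulation gave 1.78. Adjustment takes away the indirect 0.29 and then falls below the direct 1.5, because the groups compared now differ in severity.

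**The case against.** The strongest reply is that a baseline meaning was probably intended. Most of the list is baseline by nature or by wording, late enrolment means some patients will arrive with a tracheostomy, and the 17.9% describes a screening population without defining the covariate. That reading is possible. But nothing secures it: need for a tracheostomy is not the same as having one at randomization, and the neighbouring items show that the plan dates variables when it means to.

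Second, bias requires the device to change tracheostomy, and the documents do not say it does. This stands. The documents offer only an indirect route: the trial expects communication to reduce delirium, the background links delirium to longer ICU stay, and tracheostomy follows long ventilation. That is plausibility, not evidence.

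Third, the illustration puts every tracheostomy after randomization, applies a rate from patients not selected for wakefulness, and ignores the 14-day cap on the outcome. This also stands. If half of the tracheostomies came before randomization (an assumption), the shift at an odds ratio of 0.5 falls to 0.02–0.23 day, at most about 0.35 standard errors.

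Fourth, the trial is powered on the Mann-Whitney test, which suggests that the unadjusted analysis leads. The plan does not say so, and it would not make the adjusted analysis sound.

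**Conclusion.** The concern holds. The missing time point is certain, and the plan as written lets tracheostomies after randomization into the adjusted regression and the propensity fallback. Whether that biases the result depends on an effect of the device on tracheostomy that the documents neither state nor exclude, so neither the size nor the direction of a bias can be derived from them. Under the assumed models there is no material bias when the device leaves tracheostomy unchanged. A device that reduces tracheostomy would have its benefit understated, by 0.05 to 0.48 of 2.0 days at an odds ratio of 0.5; one that increases it would have its benefit overstated. These shifts are below one standard error. The unadjusted ICU-stratified test is untouched. This should be corrected because the fix is simple and the fault lies in an analysis of the primary outcome. Acute central neurological injury lacks a date too and needs the same clarification; its effect was not simulated.

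**What to change.** In the Step 2 covariate list, replace need for tracheostomy with tracheostomy in place at randomization, or drop it. Add one sentence: every variable used for adjustment or in the propensity score, including acute central neurological injury, is measured at or before randomization. Report tracheostomy after randomization by arm as an outcome; the covariate can be repaired without this, but it shows whether the device changed it.

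The cost is one phrase and one sentence. Tracheostomy status and date must be abstracted from the chart; the plan already collects procedures and charting, though it does not name tracheostomy in those lists. Any precision that later tracheostomy would have added is given up. The sample size stays at 248. The change is best made before any outcome data are seen.

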#### STEP 1: ASSESS THE SAFETY, TOLERABILITY, AND EASE OF USE OF THE EYECONTROL DEVICE

On a daily basis all patients admitted to any of the ICUs at EUH will be screened for participating in the trial. Since during admission the patient could be first excluded and later meet inclusion criteria, the screening will continue for all patients on a daily basis (for inclusion/exclusion criteria, see below).

During screening, the patients' EMR will be accessed and/or their clinical status will be discussed with the treating team (RN, APP, MD) by a member of the study team in order to identify whether they meet inclusion/exclusion criteria. For example, the study-team personnel will identify if the patient is ventilated, for how long, and what is the patient's wakefulness and cooperation by nursing charting (e.g., RASS scale, nursing neurological and clinical assessment).

Of note, due to the different nature of neurologically injured patients in these settings (primary organ effected is the brain), we will enroll about 33-50% of the patients in this step from the neuroscience ICU. This approach will allow us to consider re-defining our parameters in the second step of the trial and design a pre-defined subgroup analysis.

Upon meeting inclusion criteria, patients and/or their LARs will be approached for consent (see below for consent process details). Consented patients will be instructed how to use and operate the EyeControl device. The primary outcome of this part of the study will be time to operate the device. Successful operation will be defined as the ability to use the device to call for help, and produce one predefined sentence out of several options, three different times.

Once the patient is able to operate the device, it will stay on the patient for as long as she or he would like it on, or until the patient is successfully extubated or discharged from the ICU, whichever is earliest. During the time the patient is wearing the device, apart from its original intention to serve as a communication device, the following features will be activated and tested:

- a. Emergency call—if the patient is in distress, she or he could call for help by simply blinking three times. This will initiate a call for help from the device. We will monitor the use of this emergency call, its frequency, and causes for calling.

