- b. Wakefulness monitoring—the device will record the times in which the patient is awake by monitoring when the patient's eyes are open. This data will later be correlated with outcome measures such as delirium, LOS, and functional outcome. Changes in wakefulness time will also be correlated with ICU interventions such as adding a melatonin-agonist to promote sleep.
- c. CAM-ICU validation—every shift, after the nurse and/or study team member assesses CAM-ICU, the device will repeat the test by using multiple-choice questions and ask the patient to choose the correct answers by blinking. We will later correlate the device's results with the nursing/study team ones.
- d. Reorientation – at a defined time interval, if the patient's eyes will be open, the device will read the patient the current date/time/location.
- e. Entertainment – patients will have the option to listen to music.
- f. Family communication – Families will be supplied with a patient-unique link to record audio messages which the patient will be able to listen to through the device.

To address the secondary goal of proficiency with device operation, we will administer a daily orientation questionnaire via the device. If a patient fails this proficiency check, study staff will perform a device re-training module. The frequency and amount of necessary re-training will be captured as another data parameter.

During the study, we will collect clinical information from the patient's chart including: demographics, diagnoses, use of sedatives or medications that could change cognitive function, nursing charting (including neurological assessment), laboratory results, days on the ventilator, procedures, discharge destination, mortality, and functional outcome. All of these will be taken into account for the final analysis of the study. For example, this data could help us better identify which patients used the device more than others and which could benefit from its monitoring properties apart from its communication function.

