As part of its operation, the device captures photographs and video of the patient's eyes (figure 3). In addressing the secondary goal of potential correlation between eye behavior and clinical events, we will explore this possibility by evaluating photographs of the eyes at the times of clinical events (i.e. hypoxia, new onset shock, or new onset sepsis). The device will activate the image data collection only after 50 consecutive frames of eye-in-the-image. This should be a safety index to verify that the device is only recording the eye. It will stop recording immediately when non-eye-in-the-image occurs. Data processing to decide if an eye is in the image is done locally on the device, so eventually only images of eyes should be collected. All external image data processing will be done following deidentification of the data, using the patient code only as an identifier.

Figure 3. Example photographs captured by the EyeControl device.

No randomization or blinding is planned for this step of the study, and no samples are planned to be collected.

---

**STEP 2: MEASURE REDUCTION IN DELIRIUM-FREE AND ALIVE DAYS IN THE ICU WITH EYECONTROL-BASED COMMUNICATION COMPARED WITH THE STANDARD OF CARE.**

The second step will be similar to the operation of the first one, in terms of patient screening and enrolling. The main difference will be the randomization process. Patients will be randomized to use EyeControl for as much as they wish, versus the standard of care. Randomization will be done centrally, and will be stratified to the specific unit, gender and age, race and ethnicity.

The primary goal of the second step will be to measure the time spent alive and non-delirious in the ICU with EyeControl-based communication compared with the standard of care. Delirium will be defined as CAM-ICU positive, starting at day 1 of use (following the day of training), up to 14 days from randomization or ICU discharge, the earliest. However, patients could require moderate to deep sedation following randomization, for example due to new or evolving medical complication. Whenever the RASS is below (-1), CAM-ICU will not be measured, and will be charted as undetermined. Therefore, only days in which the patient will be CAM-ICU positive, will be counted towards the primary outcome. CAM-ICU positive days prior to randomization will not be counted towards the primary outcome.

[figure not shown]
The secondary outcomes will include the following:

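### Patients enter Step 2 at differing times after intubation, but days already ventilated at randomization is not a pre-specified covariate, which gives up some precision

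*Combined protocol and SAP*

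**What the plan says.** **Entry time varies by design.** Screening is repeated daily because a patient may become eligible late. The Sample Size section gives the example that "the patient is deeply sedated for the first few days, and later sedation is weaned", and adds: "This will allow us to recruit more patients, at different time points of their admission". The Inclusion Criteria set a minimum, "Mechanically ventilated for at least 24 hours", while Participant Selection and Sample Size speaks of two days. No maximum is given.

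**The variable is known before randomization.** Under Step 1 of Study Design and Methods, "the study-team personnel will identify if the patient is ventilated, for how long". The data listed there include "laboratory results, days on the ventilator, procedures, discharge destination, mortality, and functional outcome". The Step 2 text carries the procedure over: "The second step will be similar to the operation of the first one, in terms of patient screening and enrolling".

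**It is not used.** The covariate list (Statistical Analysis Plan, Step 2) names age, gender, race, education, unit, need for tracheostomy, "severity of illness by SOFA or APACHE score on admission and randomization day, categorical reason for admission", delirium before randomization and acute central neurological injury. Randomization is stratified by unit, gender, age, race and ethnicity. The unadjusted Mann-Whitney test is stratified by ICU only.

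**The outcome is a day count in a window that opens after randomization.** In the Synopsis (Outcome Measures) the window closes at the earliest of day 14, extubation and ICU discharge. In the Step 2 design text it closes at day 14 or ICU discharge, and extubation is not named.

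**The concern.** A count of days depends partly on how many days are available to count. If a value known at randomization predicts the length of that window, omitting it leaves explainable variation in the residual, and a chance difference between arms in that value goes unadjusted. None of the listed covariates measures prior ventilation. Need for tracheostomy comes closest, but it has no stated time point and could be decided after randomization. At stake is some precision in a trial planned at about 80% power. Adding the variable once results are known would look data-driven, so the decision belongs in the plan.

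**Working it through.** **1. The plan's sample size.** Inputs from Sample Size: difference 2 days, SD 5.2, power 80%, α 0.05 (two-sided assumed). The minimal Mann-Whitney efficiency is taken as 0.864, a value the document does not print.

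- n per arm = 2 × [5.2 × (1.960 + 0.842) / 2]² = 106.1, rounded up to 107.
- 107 / 0.864 = 123.8, so 124 per arm and 248 in total. The stated figure reproduces and is not in dispute.
- Power at 248 is 80.4%. The Synopsis gives 244, at which power is 79.7%; this does not affect the point.

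**2. Does prior ventilation predict remaining ventilation?** From the section on how many patients would benefit: "The mean number of ventilator days for patients ventilated for at least two days was 8.6, and 11.6 and 16.2" (the last two for at least three and at least five days). Mean remaining days are the stated mean minus the threshold:

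| Already ventilated | Mean total | Mean remaining |
|---|---|---|
| 2 days | 8.6 | 6.6 |
| 3 days | 11.6 | 8.6 |
| 5 days | 16.2 | 11.2 |

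**3. Are those means coherent?** The same section gives 27.8%, 18.9% and 12.6% of admissions at the three thresholds. For patients ventilated from 3 to under 5 days, the implied mean is (18.9 × 11.6 − 12.6 × 16.2) / (18.9 − 12.6) = 15.12 / 6.3 = 2.4 days. Rounding allows 2.0 to 2.8. A mean below 3 is impossible for that group. If its mean is instead set at 3 to 5 days and the other figures are held, the mean for at least five days is (219.24 − 6.3 × 3) / 12.6 = 15.9 down to (219.24 − 6.3 × 5) / 12.6 = 14.9. That leaves 10.9 to 9.9 remaining days, still above 6.6 and 8.6. The direction survives; the exact size does not.

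**4. How strong might the link be?** The documents give no correlation. As an illustration, a heavy-tailed (Lomax) distribution was fitted approximately to the figures above (shape 1.68, scale 4.49 for time beyond day 2). The window was capped at 14 days, and enrolment was assumed to occur at a constant daily hazard between 0.5 and 0.08, unrelated to remaining ventilation. The correlation between time already ventilated and window length was about 0.14 to 0.28. This is a correlation with the window, not with the outcome, and is not net of the other covariates.

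**5. What would adjustment be worth?** Suppose the partial correlation ρ with the outcome were of that size. The patient-equivalent gain is 248 × [1/(1 − ρ²) − 1]. Power uses an effective n per arm of 124 × 0.864 / (1 − ρ²).

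| ρ | ρ² | Gain (patients of 248) | Power |
|---|---|---|---|
| 0 | 0 | 0 | 80.4% |
| 0.14 | 2.0% | 5 | 81.1% |
| 0.28 | 7.8% | 21 | 83.5% |

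This is a linear-model approximation; the planned adjusted model is a median regression.

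**6. Chance imbalance.** The standard error of the difference in arm means of a standardized covariate is √(2/124) = 0.127, so a two-standard-error imbalance is 0.254 SD. The estimate would shift by ρ × 0.254 × 5.2, which is 0.18 day at ρ = 0.14 and 0.37 day at ρ = 0.28, or 9% to 18% of the 2-day target.

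**The case against.** **The retrospective means describe a different population.** They cover all patients ventilated at least two days, and only nearly 25% of those had the required RASS for at least two days. A late entrant whose sedation has just been weaned may be close to extubation, so the direction is not proven among those enrolled. This stands as a limit on the evidence. It is not a reason to omit the variable, because a continuous term can take either sign.

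**The mechanism depends on the window.** Only the Synopsis stops counting at extubation. Under the Step 2 text, prior ventilation is a weaker proxy for window length, and window length is not itself the outcome. This stands.

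**The listed covariates may already carry much of the information.** Unit, reason for admission, severity on the randomization day and tracheostomy could absorb part of the effect. This stands too, and could put the gain below the range shown.

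**The plan already has a long list, and any plan could take one more predictor.** This is fair as to weight: nothing in the plan is invalid without it. But the variable is known at screening and the protocol's own figures point to it.

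**Stronger readings that the documents do not support.** A reader might infer that the treatment estimate is biased. Allocation is randomized, so it is not biased on average; what remains is variance and unadjusted chance imbalance. A reader might also suppose that the variable explains 5–20% of outcome variance, worth 13–62 patients, but no figure in the documents supports this. Nor do they show entry weeks into ventilation: their example is the first few days, and no spread is given.

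**Conclusion.** The omission is real and worth correcting, as a modest gain in precision and robustness rather than a repair of validity. At an assumed 2–8% of outcome variance beyond the listed covariates, the gain is about 5–21 patients of 248, or 1–3 power points. It applies only to analyses that use the covariates, namely the mixed-effects median regression and its propensity-score fallback. The ICU-stratified Mann-Whitney test would not change, and the plan does not say which analysis is primary.

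**What to change.** Add days ventilated from intubation to randomization to the Step 2 covariate list, as a continuous term (for example on a log scale), before outcome data are examined. It should enter the adjusted models and the propensity-score fallback. State that the value is recorded at randomization in Step 2: days on the ventilator is listed only under Step 1 and is not itemized under Subject Hospital Data, although it can be derived from screening and ICU charting.

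Reconcile the Synopsis and the Step 2 text on whether counting stops at extubation, since the strength of this link depends on it.

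A second stratum in the Mann-Whitney test is not recommended. Splitting the six units of Table 1 in two gives 12 strata, about 21 patients each on average (248 / 12 = 20.7) and fewer in small units.

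The cost is one more term in an already large mixed-effects quantile model, which the plan itself foresees may fail to estimate. No new data collection is needed.
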